**1. PROJECT TITLE**

IRB Project #: 191398

LinkPositively: A Technology-Delivered Peer Navigation and Social Networking Intervention to Improve HIV Care Across the Continuum for Black Women Affected by Interpersonal Violence

#### **4. ESTIMATED DURATION OF THE STUDY**

3 Years (12/01/2019 – 11/30/2022)

#### **5. LAY LANGUAGE SUMMARY OR SYNOPSIS (no more than one paragraph)**

We will develop and pilot test a culturally tailored, trauma-informed smartphone app, called *LinkPositively*, for Black WLHA affected by interpersonal violence. Core components of *LinkPositively* include: a) Virtual Peer Navigation that includes phone and text check-ins and 4 weekly one-on-one video sessions to build skills to cope with barriers and navigate care; b) Social Networking platform to receive peer support; c) Educational and Self-care database with healthy living and self-care tips; d) GPS-enabled Resource Locator for HIV care and ancillary support service agencies; and e) ART self-monitoring and reminder system. Guided by the Theory of Triadic Influences and Syndemic Theory, the study will be conducted in 2 phases with corresponding aims. In Phase 1 (Aim 1), 4 focus groups with Black WLHA with experiences of interpersonal violence, one focus group with peer navigators, and 4-6 key informant interviews with providers will be conducted to determine which app features, content, and functions are most likely to support downloading, initiating use, and sustaining engagement over time. Aim 1 will culminate in usability testing by Black WLHA affected by interpersonal violence (n=8), to finalize intervention components and procedures. In Phase 2 (Aim 2), we will pilot test *LinkPositively* to assess feasibility and acceptability and determine preliminary effects of the intervention on HIV care outcomes (i.e., retention in care, ART adherence, viral suppression) and mechanism of change variables (i.e., social support, self-efficacy). Through a randomized control trial (RCT), participants will be randomly assigned to either the intervention arm (n=40) or control arm (Ryan White standard of care, n=40), with follow-up at 3- and 6- months. This study will benefit the advancement of HIV prevention science by harnessing technology to promote engagement in HIV care, while improving social support through peers and social networking—all under the auspices of being trauma-informed for Black WLHA with experiences of interpersonal violence.

#### **6. SPECIFIC AIMS**

##### **Aim 1: Develop the *LinkPositively* mobile intervention through focus groups (FGs) with Black WLHA affected by interpersonal violence, peer navigators, and service providers, and refine iterations through input from the San Diego CFAR Disparities Core CAB.**

Four FGs, with 6-8 HIV-positive Black WLHA reporting a lifetime history of interpersonal violence by an intimate partner (n=2 FGs) and non-intimate partner (n=2 FGs); one FG with 4-6 Peer Navigators employed at HIV clinics/service agencies; and 4-6 key informant interviews with service providers will be conducted in San Diego, CA. Group differences will be explored to optimize *LinkPositively* across different types of reported perpetrators. The outcomes will be feedback on proposed intervention components and suggestions for new features, as well as recommendations for how to address challenges to engagement with *LinkPositively*. Aim 1 will culminate in usability testing by Black WLHA affected by IPV (n=8), to finalize intervention components and procedures.

##### **Aim 2: Conduct a pilot randomized controlled trial to assess the feasibility, acceptability and preliminary impact of the *LinkPositively* intervention for Black WLHA affected by interpersonal violence, in preparation for a large-scale R01.**

Eighty Black WLHA ever experiencing interpersonal violence will be randomly assigned (1:1) to receive *LinkPositively* or standard of care Ryan White services, with self-reported, biological, and clinical outcomes collected at baseline, 3- and 6-month follow-up visits. Intervention use data will be collected throughout the intervention period to examine feasibility, acceptability, and the associations between components used and study outcomes. Primary outcomes are retention in HIV care, ART adherence, and viral suppression, whereas socio-structural mechanism of change variables are social support and

activation of social support networks, self-efficacy, and utilization of ancillary support services. To minimize recall bias and/or social desirability bias, that may occur with the use of audio computer-assisted self-interviews, we will use objective data to measure the main outcomes. Retention in HIV care and viral suppression will be based on medical record data and ART adherence will be measured using hair samples assayed for tenofovir and emtricitabine. The proposed study will benefit the advancement of HIV prevention science by harnessing mobile technology to promote retention in HIV care and ART adherence among US Black WLHA affected by interpersonal violence and co-occurring adverse mental health and substance abuse – an underserved, marginalized population. If the LinkPositively intervention is efficacious through an eventual R01 mechanism, it will change the paradigm for addressing the unique HIV treatment needs for Black women dually affected by HIV and interpersonal violence.

## 7. BACKGROUND AND SIGNIFICANCE

### Background and Significance

**Black women are disproportionately affected by HIV and interpersonal violence.** Black women living with HIV/AIDS (WLHA) in the US are less likely to be engaged in HIV care and adherent to antiretroviral therapy (ART) compared to other racial/ethnic groups (1-3). Black WLHA account for 61% of diagnoses among women of all races and ethnicities (4), only 56% are retained in care (1), and 49% virally suppressed (1). Black WLHA are particularly affected in San Diego County, CA, with HIV prevalence rates 8 times higher than that observed for White WLHA (5) and are underserved and understudied. Blacks on ART in San Diego are less likely to be virally suppressed than Latinos or Whites (6). Concurrently, Black women are disproportionately affected by interpersonal violence, defined as ever experiencing physical (e.g., hit, slapped, choked), sexual (e.g., forced vaginal/anal sex), and/or psychological (e.g., yelled at, belittled, controlling behaviors) abuse by a male intimate partner (e.g., spouse, boyfriend, dating partner) or non-intimate partner (e.g., relative, friend, stranger). Interpersonal violence is comprised of commonly reported forms of violence (i.e., intimate partner violence (IPV), rape, contact sexual violence, childhood abuse). Whereas the national prevalence of lifetime IPV is 45% (7), Black women report 35% higher IPV than White women (8). Moreover, although national data estimates the lifetime prevalence of rape among Black women at 21% (7), community-based samples estimate prevalence rates of rape as high as 38-54% (9-12).

**Interpersonal violence and co-occurrence of adverse mental health and substance abuse contribute to poor HIV care continuum outcomes.** WLHA experience high rates of lifetime physical, sexual, or psychological abuse (67%) (13), lifetime IPV (55%) (14-15), and past year IPV (27%) (16), a rate double the US national average. A history of abuse or trauma among WLHA is also associated with ART non-adherence, lower CD4 counts, reduced viral suppression, and increased mortality (14, 17-20). A recent study found that among HIV-positive women, those who reported recent trauma had over 3 times the odds of antiretroviral failure compared to their counterparts (17, 21). WLHA also experience co-occurring syndemic conditions with 15-24% reporting heavy or hazardous drinking of alcohol (22-23), 11-15% reporting active drug use (24-25), and 30% suffering from post-traumatic stress disorder (PTSD) (15). Black women are more likely to experience these conditions (26) than their White or Latina counterparts. In the few studies that account for co-occurring syndemic conditions using a summative score, higher syndemic scores (i.e., IPV, substance abuse, binge drinking, adverse mental health, and sexual risk-taking) were associated with poor ART adherence among HIV-positive men and women (27), and HIV-positive youth (28), and reduced viral suppression among HIV-positive women of color (29).

**Socio-structural barriers contribute to poor HIV care outcomes, whereas social support mitigates the effect.** In addition to interpersonal violence and co-morbid adverse mental health and substance abuse, Black WLHA also face socio-structural barriers affecting retention in care and ART adherence, such as HIV-related stigma and medical mistrust (30). HIV stigma is the most noted barrier to consistent access to and utilization of HIV care services for Black women (30-31). Experiences of racism, conspiracy beliefs, and the quality of relationships impact engagement in HIV medical care (32). Race-based medical mistrust predicts

lower ART adherence among Black WLHA (33). However, social support through formal and informal networks may be important to address these complex issues, and has improved engagement in HIV care among Black WLHA (34-37). Specifically, women with abuse histories are more likely to seek formal help at service agencies, after seeking support and encouragement from informal social networks (38). Studies collectively suggest that socio-structural factors, including lack of social support and HIV-related stigma, need to be considered by providers and underscore the importance of relationships and communication between patients, providers, and the support networks of Black WLHA (30).

**Mobile technology interventions to address HIV prevention are limited among women.** Given high rates of Internet access and smartphone infiltration across genders and races/ethnicities, mobile health (mHealth) technology interventions have emerged as one approach to support lifelong engagement in HIV care (32,39). Mobile technology such as mobile phones and other wireless computing devices offers advantages for women with a history of interpersonal violence such as confidentiality, more efficient and safer care, and empowerment (40-44). A majority of women (88%) in the US use the internet, with no differences in internet use by race/ethnicity (89% of Whites; 87% of Blacks) (45). In the US, cellphone ownership is highest among Black adults (98% vs 94% of White adults), and approximately three-quarters of adults across all races/ethnicities own a smartphone. Smartphone use is highly prevalent among Black individuals overall (72%) (46) and those with low socioeconomic status (85%-90% for Black women) (46-47). Moreover, 52% of Black women use a smartphone to access health information at least weekly. However, based on a 2013 review solely focused on smartphone applications (apps) for HIV/sexually transmitted disease care and prevention, most smartphone apps failed to create engaging and attractive apps (48), provided limited psychological and emotional support resources, and miss important opportunities for intervention (e.g., did not include messages about HIV prevention or medication adherence (48)). Unfortunately, these limitations to realizing the potential impact of mHealth interventions persist.

**Peer Navigation has been highlighted as a successful model of care in improving outcomes along the HIV care continuum (49).** Peer Navigators are HIV-positive, medication-adherent role models living with a similar shared experience and community membership as their target populations. Peer navigators provide social support and positive modeling of engagement-supportive behaviors to their clients, helping to build clients' self-efficacy in patient-provider communication and increase clients' trust and confidence in the health care system; offsetting the negative impact of socio-structural barriers (i.e., fear of gender-/racial-bias driving medical mistrust, stigma, and discrimination (50)) on HIV care. Peer Navigators also build clients' self-efficacy for future engagement in the HIV care system. Peer Navigation for improving retention in care among WLHA has been found to be feasible, acceptable, and efficacious in the US and low- and middle-income countries (51-55). Peer navigation has improved ART adherence and viral suppression (55-57), although some studies have found no effect (58), perhaps due to small samples or the lack of informal social support. Peer navigation with other forms of informal peer support, would likely provide greater opportunities to reduce social isolation, build community, and share strategies for addressing syndemic and other (e.g., risky sexual behavior) factors for Black WLHA. A recent analysis of messages posted on a closed Facebook group for a young adult HIV program showed that members provided high levels of emotional and social network support.

## **Preliminary Data**

**mHealth Interventions.** [name] (mPI) is currently PI on four mHealth intervention studies addressing the HIV prevention and care continuum. Thrive with Me (TWM; R01DA039950) is a responsive (i.e., adjusts to fit most devices) website that uses: informal peer support (similar to Facebook); tailored ART adherence and HIV-related information; self-monitoring of ART adherence, mood and drug use; and gamification components to improve ART adherence among HIV-positive adult MSM. Based on encouraging results of a pilot trial (59), an efficacy trial of TWM is underway in which 400 adults (age  $\geq 18$  years) HIV-positive MSM in New York City with sub-optimal ART adherence will be randomized to receive TWM for 5 months or an information-only control, and followed for 17 months. An interim analysis of community wall posts found that HIV-positive MSM spontaneously initiated discussions with each other on sensitive topics, such as ART adherence and sexual risk reduction strategies, and provided informational and emotional support to one

other (60). As part of the UNC/Emory Center for Innovative Technology (iTech), within the new Adolescent Trials Network (ATN), TWM is being adapted for and subsequently tested among 350 HIV+ youth (15-17 years) and young adults (18-24 year; U19 HD089881). Also, as part of ATN's iTech, the team is leading a technology-based stepped care intervention for transgender and gender non-binary youth to reduce sexual risk behavior and increase PrEP uptake through tailored SMS messages, a culturally-tailored mobile app, and individualized e-coaching (U24 HD5109014). Finally, [name] recently completed a native app (available on iOS and Android) intervention to increase regular HIV testing.

**Peer Navigation.** The BRIDGES Project (PI: [name]; Consultant: [name]; California HIV/AIDS Research Program; HD15-SD-059) is a Peer Navigation RCT intervention among Black and Latina women in San Diego, CA that provides trauma-informed Peer Navigation to improve linkage to and retention in HIV care and ancillary support services. Upon completion of the pilot test, women reported improvements in coping self-efficacy, self-efficacy to activate social support networks, and had increased retention in HIV care over a 3-month period (61). [name] (Consultant) leads an HIV service organization (WORLD) in Oakland, CA, that has implemented peer navigation services into their programs. The Peer Advocate program at WORLD hires Peer Navigators, including Black WLHA – with life experiences similar to the women they serve (e.g., histories of physical, sexual, and psychological abuse; adverse mental health; substance abuse) – who provide emotional and practical support to WLHA, and help them navigate the medical and social services systems. [name] and WORLD led a peer navigation intervention (Kaiser-funded study) to improve engagement in HIV care and ART initiation among out-of-care HIV-positive women of color. Of the 84 women enrolled (62), 48% experienced lifetime physical abuse, 42% experienced lifetime sexual assault, 29% used substances in the past month, and 29% had attempted suicide. At 6-month follow-up, women in the intervention group had less missed HIV care visits and more access to ancillary services than women in the control group (Ryan White case management services). In both groups, there were increases in the proportion of women initiating ART. These findings demonstrate the utility of a peer-based navigation program in improving retention in HIV care and ART uptake.

## 8. PROGRESS REPORT

N/A.

## 9. RESEARCH DESIGN AND METHODS

**Study Overview:** This study will be conducted in 2 phases, corresponding to the study aims:

Phase 1 (Aim 1): Developing LinkPositively with input from Black WLHA with a lifetime history of interpersonal violence, peer navigators, and providers, and the San Diego Center for AIDS Research (CFAR) Disparities Core Community Advisory Board (CAB). Phase 1 will culminate in usability testing, Beta Testing, by Black WLHA affected by interpersonal violence (n=8), to finalize intervention components and procedures.

Phase 2 (Aim 2): Piloting an RCT to evaluate feasibility, acceptability, and the preliminary effect of LinkPositively among Black WLHA with a lifetime history of interpersonal violence. This multi-component, culturally tailored, and trauma-informed mHealth intervention will primarily aim to increase retention in HIV care, ART adherence, and viral suppression for Black WLHA affected by interpersonal violence. The four components of LinkPositively will achieve these aims directly by improving self-efficacy for coping, social support networks, and utilization of ancillary support services (i.e., domestic violence, mental health, substance abuse), and indirectly by reducing HIV stigma and medical mistrust.

**Study Setting:** The study will take place in three California counties (San Diego, Los Angeles, and Alameda) and two Oklahoma counties (Oklahoma and Tulsa). In San Diego County, between 1981 and 2011, the proportion of AIDS cases among White persons dropped (70% to 42%) while the proportion of cases among people of color increased considerably (19% to 58%). While African American persons represent 5% of the county's population, they make up 13% of individuals diagnosed with HIV. Moreover, the AIDS rate is almost 8 higher among African American women, compared to White women. Similar HIV prevalence rates are

observed for African American women in other counties in California (Los Angeles and Alameda) and Oklahoma (Oklahoma City and Tulsa), with African American women disproportionately affected.

### **Study Population:**

#### **AIM 1**

In Phase 1 (Aim 1), eligible participants for the focus groups and interviews will be: (1) Black WLHA (including transgender women) with a history of interpersonal violence (n=6-8 per FG; total of 4 FGs); (2) Black WLHA (including transgender women) with a history of interpersonal violence who act in a professional capacity as a Peer Navigator (n=4-6; one FG); and (3) Key Informants (n=4-6) will be leadership at local clinics and community-based organizations known to provide services to women in the areas of HIV/AIDS care and domestic violence services, such as UCSD Owen Clinic and Mental Health America. Phase 1 will culminate in usability testing, Beta Testing, by Black WLHA affected by interpersonal violence (n=8; 4 with histories of interpersonal violence perpetrated by a current or former intimate partner and 4 with histories of interpersonal violence perpetrated by a non-intimate partner [e.g., family member, friend, stranger]), to finalize intervention components and procedures.

#### **AIM 2**

In Phase 2 (Aim 2), eligible participants for the RCT will self-report: (a) female gender (including transgender women), (b) Black or African American racial/ethnic background, (c) aged 18 years or older, (d) HIV-positive status, (e) ever experienced physical, sexual, and/or psychological abuse by a current or former partner or non-partner (e.g., relative, friend, stranger), (f) owner of a smartphone with internet browsing capabilities, and (g) English speaking. Purposive sampling will be used to ensure that groups are balanced with respect to type of perpetrator (current or former intimate partners [e.g., spouse, boyfriend, dating, casual] and non- intimate partners [e.g., family member, friend, stranger]) and retention in HIV medical care status (linked to care but have fallen out of care [i.e., no ART prescription filled, no viral load labs, or no HIV care visits with an ART-prescribing provider in the past year] versus linked to and retained in care [i.e., ART prescription filled, viral load labs, or HIV care visits with an ART prescribing provider in the past year]).

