## **AIM 2**

In Phase 2 (Aim 2), we will conduct the pilot RCT with 80 women from the study population. Potential participants will be recruited through community contacts across San Diego County, Los Angeles County, Alameda County, Oklahoma City County, and Tulsa County. Members of the research team have established relationships with the following key organizations that provide HIV testing and/or treatment to WLHA and these organizations are represented through membership in the San Diego CFAR Disparities Core CAB: UCSD Owen Clinic, UCSD Mother, Child and Adolescent HIV Program, Family Health Centers of San Diego, San Ysidro Health Center. We will also extend recruitment to Black WLHA through presentations at organizations providing HIV-related services such as Mental Health America San Diego, Neighborhood House Association, and the Center for Community Solutions Rape Crisis Center. In Los Angeles County, we will recruit from the following community-based organizations: UCLA Family AIDS Network, AIDS Project Los Angeles, Maternal Child Adolescent Clinic, OASIS Clinic, East LA Women's Center, Alta Med, and JWCH Institute. In Alameda County, we will recruit from WORLD, an HIV service organization for women of color. In Oklahoma City and Tulsa Counties, we will recruit from Guiding Right, Inc., a Black-focused community-based organization. In all counties, we will distribute flyers and advertisements through street outreach efforts, community events, and newspapers such as the Voice and Viewpoint, an African American locally based newspaper. Finally, we will employ Facebook Advertising to recruit women through social media, including on the platforms Facebook and Instagram, and using the Facebook Audience Network to run advertisements on other websites the target population is likely to utilize. We have successfully utilized these recruitment efforts in previous studies. Further, we will employ Build Clinical, an organization that assists academic researchers in study enrollment through technology and novel data-driven approaches.

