or to a secure survey via Build Clinical. The survey link will first notify potential participants that by continuing to the study screener, they are providing consent to be screened digitally. If consent is obtained, then a 10-minute screener will be conducted to assess eligibility. Screening questions will include age, biological sex, gender identity, self-reported HIV status, and measures pertaining to lifetime trauma, mental health, post-traumatic stress, past year physical and/or sexual violence, and substance and alcohol use. Due to the highly sensitive nature of this study, ability of potential participants to screen digitally will reduce participant burden in the screening process and increase participant options in the screening process, as is aligned with a trauma-informed approach to working with WLHA.

After eligibility is determined, eligible participants who screened through REDCap will be asked to provide the study staff with their contact information (phone number, email address), along with the names and corresponding contact information (e.g. phone number) of up to 3 individuals who may be contacted if the research team is unable to contact the participants for study initial visits and/or follow-up visits. The research team will only contact these alternative contacts if we cannot reach the participants through 10 attempts (total) on different days and times using the contact details that the participants provided the research team. Eligible participants who are recruited through Build Clinical will provide contact information through the secure participant management platform, which is kept secure using server authentication and data encryptions that are the same as those used in healthcare institutions. Data is transmitted via HTTPS, and Build Clinical uses a Transport Layer Security (TLS) 1.2 with a 2048-bit server key lengths and industry-leading modern browsers. No subject data other than eligibility screening data is stored by Build Clinical. All servers are based in the US, and data will be deleted upon request from the UCSD research upon closing of the study. The screening survey used through Build Clinical is identical to that used in REDCap.

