### **Medical Record Chart Abstraction**

During the passive follow-up period (7-12 months post-baseline), the research team will utilize the signed Release of Information (ROI) forms and HIPAA Authorization Forms of all study participants (participant consent collected at Baseline Study Visit), in order to request medical chart data for all participants from local HIV care providers to obtain data on clinic visits, HIV viral load, and CD4 values. Data will be entered into the REDCap Electronic Data Capturing System. These medical chart data extractions will be conducted periodically, given the staggered enrollment period.

To safeguard confidentiality, for the quantitative data collection, each participant will receive a unique patient identification number (PID) and names will never be used in conjunction with PID numbers. This unique PID number will appear on the survey, tracking forms (e.g., scrip payment receipt, cell phone tracking form), locator and screening forms. Participant confidentiality will be maintained through use of the unique PID and secure networks where data are stored. All laboratory data will be electronically transferred to the UCSD Data Management Center via password protected electronic files. At the UCSD Data Management Center, all computer files will be identifiable only by the PID number.

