### **Intervention Trial:**

**Treatment Conditions.** Following the Baseline Visit, participants will be randomized at a 1:1 ratio to an intervention arm or control arm. The Biostatistician team will generate the randomization sequence to ensure that randomization occurs independent of the core research team. Participants will be informed of their study group assignment immediately after completion of their baseline survey.

**Control Arm.** Women assigned to the control arm will be connected with and will receive self-directed (non-Peer Navigation supported) treatment as usual at agencies and institutions in San Diego, Los Angeles, Alameda, Oklahoma City, or Tulsa County following the Ryan White HIV/AIDS Program standard of care (i.e., referrals to physical, dental, and mental health services; medical case management; and ancillary services [e.g., alcohol/substance use recovery, family support]). Women who are not already receiving services and do not have other means of receiving services or are not under medical case management elsewhere will be referred to care. Alternatively, women may request case management services via Ryan White HIV/AIDS Program at a preferred location.

Using the Ryan White standards of care, goals will be set to create an individual care plan related to medical care, housing, financial, and other resources as needed. Referrals will be made to appropriate services (e.g., primary care, housing, benefits counseling, transportation, food, legal services, support services) based on intake interview. Women who require a higher level of care (e.g., significant mental health concern, at risk or falling out of care) and do not have other means of receiving services or are not under medical case management elsewhere may request case management services via Ryan White HIV/AIDS Program in San Diego, Los Angeles, Alameda, Oklahoma City, or Tulsa County.

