#### **Inclusion criteria:**

- Aged 18 years or older
- Self-identification as a cis-gender or transgender woman
- Self-identification as Black or African American
- Living with HIV/AIDS
- Ability to speak and understand English
- Ever-experienced physical, sexual, and/or psychological abuse by a current or former partner or non-partner
- Owner of a smartphone with internet browsing capabilities

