## **20. COMPENSATION FOR PARTICIPATION**

Participants will receive compensation, once completing each of the following:

Phase 1 (Aim 1):

- Focus Groups (\$50) [24-32 participants]
- Key Informant Interviews (\$50) [4-6 participants]
- Beta Testing (\$50) [8 participants]

Compensation for Phase 1 participants will be \$50 total.

Phase 2 (Aim 2):

- Baseline Study Visit (\$25) [All participants]
- Follow-Up 1 Study Visit (3 months post-Baseline) (\$30) [All participants]
- Follow-Up 2 Study Visit (6 months post-Baseline) (\$40) [All participants]
- Completion of all Study Visits (\$10) [All participants]
- Hair Sample Collection at Baseline, Follow-up 1, and Follow-up 2 (\$25 at each visit) [All participants]

Compensation for Phase 2 participants will be up to \$180.

Additionally, we will provide assistance to participants in accessing transportation to study visits in the form of a) a public transportation day pass that can be used on local buses and light rail trains throughout San Diego, Los Angeles, Alameda, Oklahoma City, or Tulsa County or b) a scheduled ride between a location of the participant's choosing to the study visit location, using rideshare service Lyft Concierge, provided via the existing University of California San Diego contract with Lyft Concierge. Should a participant choose to be provided with a ride by Lyft Concierge, the reason for the participant's visit to the study visit location will not be disclosed.

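### HIV-positive status is self-reported and not confirmed before randomisation, and the plan does not say how a woman with no HIV record is scored on the primary outcomes

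*Combined protocol and SAP*

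**What the plan says.** **Eligibility.** In Section 9, Study Population, Aim 2, the criteria begin "eligible participants for the RCT will self-report", and HIV-positive status is item (d). Section 10, Aim 2, repeats this. The inclusion list in Section 10 says only "Living with HIV/AIDS", and neither exclusion criterion concerns unconfirmed status.

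**Screening and recruitment.** Section 9, Study Screening and Enrollment, Aim 2, describes the digital screener: "Screening questions will include age, biological sex, gender identity, self-reported HIV status" and several psychosocial measures. The same section names many HIV clinics and service organisations, and adds that "we will employ Facebook Advertising to recruit women through social media". It also uses a commercial recruitment platform. Section 20 states "Compensation for Phase 2 participants will be up to" 180 dollars.

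**Order of events.** The baseline visit consists of consent, survey and hair collection. Then, under Intervention Trial, "Participants will be informed of their study group assignment immediately after completion of their baseline survey". Release and HIPAA forms are signed at baseline, but the chart-abstraction section places the record requests in months 7 to 12.

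**Outcomes.** Section 6, Aim 2, names retention in care, ART adherence and viral suppression as primary. Retention and suppression come from medical records, and adherence from tenofovir and emtricitabine in hair. The SAP, under Intervention Impact, gives medians, interquartile ranges and frequencies by group. It sets no success threshold and no rule for a missing record.

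**The concern.** Every primary outcome is meaningful only for a woman who has HIV, yet the one criterion that guarantees this rests on her word. The protocol is cautious about self-report elsewhere: Section 6 chooses objective outcome data because of recall and social desirability bias. The means of checking status are in hand on the day of enrolment, since the releases are signed then, but they are not used for that purpose.

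A woman without HIV would plausibly have no HIV visits, no HIV viral load and no antiretroviral in hair. The trial also deliberately samples women who have fallen out of care, and some of them will show the same picture over the past year. Unless the basis of eligibility is recorded at entry, a result of no chart found is hard to read.

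There is also a point outside the statistics. The app's peer feed is meant for women living with HIV, and Section 14 notes that some may disclose their status there for the first time. Aliases and daily monitoring reduce this exposure, but they do not check who has joined.

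**Working it through.** **The plan's own figures.** The 180 dollars reproduces: 25 + 30 + 40 + 10 + 3 × 25 = 180. The sample size of 80 (40 per arm) is given without alpha, power or effect size, so it cannot be reproduced.

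**Inputs.** 40 women per arm (Section 10, Aim 2). Background viral suppression of 49% (Section 7), used for illustration only. The misclassification rate is not in the documents, so 1, 2 or 4 women per arm, or 2.5%, 5% or 10% of each arm, are assumptions.

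**Weight of one woman.** 1/40 = 2.5 points. If 80% of an arm is followed (32 women), 1/32 = 3.1 points.

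**Level of one arm, by scoring rule.** With k women without HIV among 40:
- scored as failures: 0.49 × (40 − k)/40
- an undetectable viral load scored as suppressed: [0.49 × (40 − k) + k]/40
- missing or excluded: 49%, on a smaller denominator

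| k | Failure | Suppressed | Missing |
|---|---|---|---|
| 1 | 47.8% | 50.3% | 49% |
| 2 | 46.6% | 51.6% | 49% |
| 4 | 44.1% | 54.1% | 49% |

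The direction of the error therefore depends on a rule that the SAP does not state.

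**Dilution of the difference.** Let a fraction m of each arm be without HIV, all scored the same way. The difference becomes (p2 − p1)(1 − m), whether they are all failures or all suppressed, because the added constant cancels. An assumed 20-point difference (49% against 69%) becomes 19.5, 19.0 or 18.0 points at m = 2.5%, 5% or 10%. With the women scored as failures, 40 per arm and two-sided alpha 0.05, power would be 44% with no misclassification and 42%, 40% or 36% at those three values. The SAP plans no test, so the power figures only show scale.

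**Chance imbalance.** Suppose 4 of the 80 are without HIV and 40 go to each arm:
- P(2 and 2) = C(40,2)² / C(80,4) = 608,400 / 1,581,580 = 38.5%, so P(arms differ by 2 or more) = 61.5%, about 62%.
- P(all 4 in one arm) = 2 × C(40,4) / C(80,4) = 182,780 / 1,581,580 = 11.6%, about 12%.

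If all four fell in one arm and were scored as failures, that arm would be expected to move from 49% to 44.1%, about 5 points. The full 10 points (4 × 2.5) would require that all four places would otherwise have been successes.

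**The case against.** Four arguments on the other side have weight.

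- **Risk is limited at entry.** Much recruitment runs through HIV clinics and HIV service organisations. Baseline is planned in person, with an interviewer asking about treatment, medication and source of care. The rate may well be low. This stands, but it does not replace confirmation, and Section 12 seeks permission to enrol by phone or video if in-person work is not possible.
- **Objective evidence exists before the charts.** Hair for antiretroviral assay is taken at baseline. Drug in that sample would support HIV status for women on the assayed drugs. So a reader who infers that the month 7 to 12 charts are the first independent evidence would be wrong. The assay is not described as an eligibility check, however, and it cannot help for women off ART.
- **Older records help.** Both care strata are defined as linked to care, and the out-of-care group is defined by gaps in the past year only. No look-back limit is set for the chart request, so earlier records would separate many of these women from a woman without HIV. The inference that an ineligible woman can never be identified afterwards is therefore too strong. What stands is that later data may not always do it.
- **This is a descriptive pilot.** The expected effect on a difference is modest. That is true, but with no test planned, a shift of a few points would be read directly as a trend.

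**Conclusion.** The gap is real: HIV status is accepted on self-report, and the available text describes no confirmation before assignment. Some pages are not in that text, so the absence is limited to what can be read.

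A reader might infer that a woman without HIV would count as a failure on all three primary outcomes. The documents do not support that. With no threshold and no missing-data rule, she could be a failure, be missing or, if a viral load were run, be counted as suppressed.

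The size is up to 2.5 points per woman in an arm of 40. Because randomisation equalises misclassification in expectation, the expected effect is dilution (20 points to 19 at an assumed 5%), with chance imbalance on top (62% for a difference of two or more if 4 of 80 are affected). A shift of 5 to 10 points from 2 to 4 women is a ceiling, since it needs all of them in one arm and every place otherwise a success. All of these figures rest on assumed rates. The change is worth making because it is cheap and makes later missing records interpretable.

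**What to change.** In Section 9 (Study Population, and the enrolment text under Study Screening and Enrollment, Aim 2) and Section 10 (Aim 2), replace self-report alone with confirmation before randomisation from any one existing source:

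- a labelled ART bottle
- a laboratory or clinic letter
- a patient-portal view
- confirmation by a current or past HIV clinic, or by the referring agency, under the release signed at baseline

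Allow the source to be shown remotely when enrolment is by phone or video. When no source is at hand, hold randomisation rather than exclude the woman. Record which source was used. In the SAP, state how a woman with no HIV record is scored on each primary outcome.

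The SAP is written in the past tense. If enrolment is already complete, report by arm how many women had any chart evidence of HIV, and apply the check in the larger trial that Section 6 foresees.

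**Cost.** No new test or staff. Because assignment and app training are tied to the baseline visit, holding randomisation means a second contact and a short delay for some women. This falls mainly on those out of care, whom the trial wants to reach, so the list of acceptable sources should stay broad.
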